10.2. Data Screening and Acceptance

All data involved in the determination of endpoints will be screened for missing and unusual values. Any missing data affecting the ability to determine or analyze any endpoint will be queried by Data Management for confirmation of irretrievability. Unusual values, such as outliers, are also to be queried, and if confirmed, will be used as recorded.

10.3. Glossary of Terms and Abbreviations

The Clinical Protocols provide a current Glossary of Terms and Abbreviations.

APPENDIX A – DATA HANDLING AND ANALYSIS

This appendix provides additional details on the data handling and analysis of the study data.

Incomplete Data

If a date needed for calculation (e.g., date of birth for age) is an incomplete date (e.g., **112006 or ****2006) it will be completed as follows:

For incomplete event dates '01' or '0101' will be entered, respectively (worst case).

However, if an imputed event date is before the date of procedure, the date of event will be set equal to the date of procedure.

For all other incomplete dates '15' or '0107' will be entered, respectively (less far from correct date). If the missing month is known to be between July and December, the month September will be used.

If the entire start date of an event or a medication is missing, the procedure date will be imputed. Imputed dates will be limited to date of birth, AE start date, and medication start and end dates.

General Analysis Definitions

Assessments will be presented chronologically by study day, which is defined in the following:

Study day= assessment day – date of index-procedure.

Index-procedure day = 0. Events occurring on the day of the index-procedure will be considered day 0.

Events occurring on the day of discharge will be considered in-hospital.

Time of follow-up = date of last contact – date of index procedure. Where date of last contact is date of death or the latest of: date of last adverse event, date of last procedure, or date of last-follow-up visit.

Events will be reported as days elapsed since index procedure, or **Event Day** = event start date – index procedure date. Partial or missing dates will be imputed based on the rules described above. This approach avoids bias that increases with time since index procedure, as well as any confusion that may occur during event adjudication. For analysis at each time point, subjects will be censored at the time point or time to follow-up as defined above, whichever is earlier.

For all the clinical endpoints, the denominator will include subjects who either have an adjudicated event (e.g., death, revascularization) before the time of interest, or have a contact beyond the lower window of the follow-up.

Specific Reporting Conventions

Two types of endpoints will be reported – Clinical/safety endpoints and Core lab endpoints.

A. Clinical/Safety Endpoints

Clinical endpoints include repeat revascularization procedures on target lesions/vessels, death, target limb amputations, and safety endpoints including Major Adverse Events, that occur within a specific time period. For each reporting period, the event rate will be defined as the number of subjects experiencing the event divided by the number of evaluable subjects. A subject will be considered evaluable for a reporting period if the study day of last contact is at or after the lower limit of the reporting window on the snapshot date. Acceptable study contacts include a study visit, adverse event, CEC adjudicated event date, image date, or other verifiable event that occurs during the active follow-up of a subject. Active follow-up ends when a subject completes the study, withdraws consent, or is considered lost to follow-up.

B. Core Lab Endpoints

Core lab endpoints include the endpoints that are determined by core lab assessment (duplex ultrasound or angiography), such as restenosis measured by duplex ultrasound or residual stenosis by angiography. Core lab endpoints rely on the actual evaluable assessment. If the scheduled assessment is not completed or the data are not evaluable (i.e., not readable or non-diagnostic), it will be treated as missing value and excluded from the analysis. Data will be used for subjects who have an evaluable (readable or diagnostic) scheduled duplex ultrasound.

C. Determination of Primary Patency Composite Effectiveness Endpoint

Primary patency contains both core lab endpoint (by visit) and clinical/safety endpoint (by cut-off days); the event of the individual component will be determined first, and the composite endpoint will then be determined.

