1. INTRODUCTION

This statistical analysis plan (SAP) outlines the data and procedures used for assessing the safety and effectiveness of the Shockwave Medical JAVELIN Peripheral IVL Catheter over pooled data from two studies: the Mini S Australia and New Zealand Study (CP65324) and the FORWARD IDE Study (CP67398).

Data from subjects enrolled under the IDE protocol will be pooled with data from the Mini S Australia and New Zealand Study to form a pooled primary analysis cohort of 90 subjects. Results of the first 90 consecutively enrolled subjects with evaluable data across both studies (with a minimum of 50% of patients from the US) will comprise the primary analysis cohort and will be submitted to FDA to support a Premarket Notification 510(k) application for the JAVELIN IVL Catheter. Results of the full cohort from both studies in up to 125 subjects will be provided to FDA in annual progress reports.

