4.3. Secondary Endpoints

- **Serious angiographic complications** defined as flow-limiting dissection (\geq grade D), perforation, distal embolization, or acute vessel closure as assessed by the angiographic core lab.
- **IVL Technical Success (post-dil)** defined as *post-dilatation* residual stenosis $\leq 50\%$ without flow-limiting dissection (\geq Grade D) of the target lesion by angiographic core lab (measured immediately following mandatory post-dilatation).
- **IVL Device Success** defined as the ability to deliver, advance across the target lesion, pressurize, pulse, flush and retrieve the JAVELIN IVL Catheter.
- **Technical Success (final)** defined as *final* residual stenosis $\leq 30\%$ without flow-limiting dissection (\geq Grade D) of the target lesion by angiographic core lab.
- **MAE** at 6 and 12 months (as a composite and individual components)
- **Primary Patency** at 12 months defined as:
 - Above the knee lesions: freedom from $\geq 50\%$ restenosis as determined by Duplex Ultrasound (DUS) and freedom from Clinically-Driven Target Lesion Revascularization (CD-TLR)
 - Below the knee lesions: freedom from both total occlusion (100% diameter stenosis by DUS) in all of the target lesions in a flow pathway, as well as a CD-Revascularization (CD-TLR).

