9.3. Handling of Dropouts and Missing Data

No imputation of or adjustments for missing data will be performed for the primary analyses. All available data will be presented. For time to event analyses, subjects who do not experience the event in question will be censored at their last known follow-up.

For the primary safety endpoint analysis, the denominator for each parameter in the safety measures will be the number of subjects who had sufficient follow up (at least 23 days for 30-day visit) plus any subjects who had an event prior to the milestone visit.

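### SAP Appendix A sets two conflicting denominators for 6- and 12-month MAE: one overstates the rate when follow-up is incomplete, the other drops early cardiovascular deaths

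*SAP*

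**What the plan says.** MAE at 6 and 12 months, as a composite and by component, is a secondary endpoint (SAP 4.3) with no hypothesis or performance goal. Appendix A governs how the rate is formed, in two places.

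- **General Analysis Definitions:** for every clinical endpoint, "the denominator will include subjects who either have an adjudicated event" ahead of the time point in question. An event-free subject counts only through a contact later than the lower limit of the visit window.
- **Specific Reporting Conventions, Clinical/Safety Endpoints:** "the event rate will be defined as the number of subjects experiencing the event divided by the number of evaluable subjects". It then defines evaluable: "A subject will be considered evaluable for a reporting period if the study day of last contact is at or after the lower limit". That limit is the one for the visit window, and the check is made as at the date of the data snapshot. There is no exception for a subject who has already had an event.

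The protocol's Table 1 puts the lower limits at day 150 (180±30) and day 330 (360±30). Appendix A takes the date of death as the date of last contact for a subject who dies.

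SAP 9.3 adds a censoring rule: "For time to event analyses, subjects who do not experience the event in question will be censored at their last known follow-up". Appendix A has a similar one. Neither is tied to a named endpoint, and no time-to-event estimator is named.

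On reporting, SAP 1 states: "Results of the full cohort from both studies in up to 125 subjects will be provided to FDA in annual progress reports".

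**The concern.** Under the general definition, a subject lost at month 4 counts if an MAE came first and disappears otherwise. The same happens to a subject who is not yet due at the snapshot date. Inclusion depends on the outcome, and the ratio is pushed up.

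Under the reporting convention, that asymmetry largely goes for non-fatal events, but a cardiovascular death on, say, day 100 sets last contact at day 100, so the subject is not evaluable at 12 months. Cardiovascular death is itself an MAE component (SAP 4.1).

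Two analysts following the SAP could therefore report different longer-term safety rates from the same data, one too high and one with deaths missing. At stake is how the 6- and 12-month safety results are read by FDA and the data and safety monitor. Study success is not at stake.

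**Working it through.** **1. The plan's own figure.** The documents give no 6- or 12-month rate or precision, so the only stated figure to reproduce is the power at n = 90, one-sided 0.025, exact binomial (SAP 6.1-6.3).
- Safety: reject at 4 or fewer events; exact alpha 0.0218 at 11.2%, power 96.5% at 2.0%.
- Effectiveness: reject at 84 or more successes; exact alpha 0.0131 at 85.0%, power 98.1% at 97.0%.
- Product: 0.9652 × 0.9812 = 0.947, as stated.

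**2. Final data under the general definition.** Assumptions, since the documents give none: exponential event and dropout times, true 12-month event rate p, 12-month dropout d. Let λ = −ln(1−p)/360, μ = −ln(1−d)/360, s = λ+μ.
- Observed events: E = (λ/s)(1 − e^(−360s))
- Denominator: D = (λ/s)(1 − e^(−330s)) + e^(−330s)
- Crude rate: E/D

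With p = d = 0.10, 360λ = 360μ = 0.1054 and 360s = 0.2107. Then E = 0.5 × (1 − 0.8100) = 0.0950, D = 0.5 × (1 − 0.8244) + 0.8244 = 0.9122, and E/D = 10.4%.

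| True rate | 5% dropout | 10% | 20% |
|---|---|---|---|
| 12 months, 10% | 10.2% | 10.4% | 10.9% |
| 12 months, 20% | 20.4% | 20.8% | 21.6% |
| 6 months, 10% | 10.1% | 10.2% | 10.4% |

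For scale, one standard error at 10% is √(0.1×0.9/90) = 3.2 points, or 2.7 points with 125 subjects.

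**3. A snapshot before follow-up closes.** Follow-up is also cut at the snapshot date. Inputs: 75 IDE subjects entering uniformly over 12 months (protocol 6.2, 6.3), and 50 Mini S subjects past their 12-month window (protocol 3.1.3 says up to 50; that all are complete is an assumption). True 12-month rate 10%, dropout 10%, months of 30.4 days. The proportions in step 2 are averaged over entry dates.

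| Months after first IDE enrolment | Expected events | Event-free, evaluable | Pooled crude rate | IDE subjects alone |
|---|---|---|---|---|
| 15 | 10.0 | 62.0 | 10.0/72.0 = 13.9% | 19.9% |
| 18 | 11.1 | 77.4 | 11.1/88.5 = 12.5% | 14.8% |
| 24 | 11.9 | 102.1 | 11.9/114.0 = 10.4% | 10.4% |

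**4. The reporting convention.** With non-fatal events only, the 12-month snapshot rate stays at 9.7-10.0% for a true 10%. With deaths, let M of N subjects have an MAE, K of them by cardiovascular death before the lower limit. Taking the numerator from evaluable subjects, as a proportion requires, the rate becomes (M−K)/(N−K). This is below M/N whenever K > 0 and M < N.

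**5. Estimators compared.** Simulation, 4,000 runs, the pooled cohort of step 3 at month 18, 10% dropout, 15% 12-month MAE risk before competing deaths.

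| Non-cardiovascular death by 12 months | Truth | Crude | 1 − Kaplan-Meier | Aalen-Johansen |
|---|---|---|---|---|
| None | 15.0% | 18.6% | 15.0% | 15.0% |
| 10% | 14.3% | 17.2-19.3%* | 15.0% | 14.2% |

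*Depending on whether these deaths are in or out of the denominator.

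The standard deviation at month 18 was 4.0-4.4 points for the crude rate and 3.4-3.5 for Aalen-Johansen, so precision is not lost.

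**6. The 30-day endpoint.** With 5% dropout by day 30, a true 2.00% is reported as 2.03%. SAP 9.3 expressly keeps subjects with an event in the 30-day denominator, so the conflict does not reach the primary test.

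**The case against.** The best defence is that this is a descriptive secondary endpoint and that in completed data the bias is well inside one standard error. The general definition errs against the device, censoring rules already exist, and many kinds of contact count towards evaluability. All of this stands, and it limits the weight of the point.

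It is also fair that the upward bias is not settled, because the reporting convention read literally removes most of it for non-fatal events. But that reading loses early cardiovascular deaths, and nothing in the SAP says which text governs at 6 and 12 months. The 30-day wording in 9.3 suggests that events are meant to be kept, but it is limited to the primary endpoint.

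Three stronger inferences are tempting and not supported:
- **That annual reports will carry a badly inflated 12-month rate.** The snapshot wording allows an early rate, but no text says that one will be shown. Figures near 20% describe IDE subjects alone, whereas SAP 1 has the reports cover both studies.
- **That event-free subjects need complete follow-up to count.** They need a contact beyond the lower window limit.
- **That Kaplan-Meier cures this at no cost.** It censors non-cardiovascular deaths and so runs high when they occur (15.0% against 14.3% in step 5).

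The fear of a false safety signal should also be kept in proportion: protocol 13.2 ties no monitoring rule to this ratio.

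**Conclusion.** The point holds as a conflict between two denominators, neither of which is satisfactory. The general definition overstates MAE when follow-up is incomplete. In final data the excess is under 1 point at a true 10% and up to 1.6 points at a true 20% with 20% dropout. It is about 4 points at month 15 and 2.5 points at month 18 if a pooled 12-month rate is shown early. The reporting convention understates MAE by leaving out early cardiovascular deaths, by an amount that depends on their number.

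These sizes rest on assumed event rates, dropout, constant hazards, uniform accrual and a completed Mini S cohort. If fewer Mini S subjects were complete, the pooled snapshot figures would be higher. A reader might infer that the primary safety result or the 94.7% power is compromised; both are essentially unaffected. The change should be made, because longer-term safety rates should not depend on which paragraph the analyst follows.

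**What to change.** In SAP Appendix A:
1. Reconcile the denominator in General Analysis Definitions with the definition of evaluable under Clinical/Safety Endpoints, and state that a subject with an adjudicated event, including death, is never dropped for short follow-up.
2. Report 6- and 12-month MAE and its components as Aalen-Johansen cumulative incidence at days 180 and 360, with 95% confidence intervals and numbers at risk, using the existing censoring rules. For MAE, non-cardiovascular death is a competing event. For CD-TLR and amputation, any death is. For cardiovascular death, non-cardiovascular death is.
3. Keep the crude ratio only as a secondary display, restricted to subjects whose potential follow-up (index procedure to snapshot date) has reached the window, with early deaths kept in.
4. Leave the 30-day primary test as it is.

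The cost is SAP wording and a little more analysis. Event dates, last-contact dates and adjudicated events are already collected, and no subjects are added. What remains is the assumption that censoring is non-informative; numbers at risk let the reader see how much of the estimate rests on it.

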7.7.1 Procedural Imaging Requirements

An angiographic cine will be obtained at four (4) timepoints for each target lesion as follows:

1. Pre-procedure (include run-off the foot)
2. Post-JAVELIN (immediately following treatment with JAVELIN and before post-dilatation)
3. Post-Dil (following mandatory post-dilatation)
4. Final (end of procedure, include run-off to the foot)

If any non-target lesions are treated, an additional cine will be obtained prior to IVL treatment of any target lesion(s) to ensure no serious angiographic complications have occurred and that the patient still meets criteria to be enrolled. All angiographic images must be submitted to the core lab for analysis. If intravascular imaging (including IVUS or OCT) is performed as standard of care, images from the four timepoints (pre-procedure, post-JAVELIN, post-dil and final) should be submitted to the Sponsor for analysis.

Core lab training materials will be provided with detailed instructions on the image acquisition process.

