9.4 Analysis Populations and Poolability

The primary analysis population for the FORWARD PAD IDE study will be the Intent-to-Treat (ITT) cohort which includes all enrolled subjects.

The FORWARD PAD IDE study is being conducted to supplement enrollment in the ongoing Mini S Study described in Section 3.1.3; data from subjects enrolled under the IDE protocol will be pooled with data from the Mini S Study to reach a total sample size of 90 subjects. Results for the first 90 consecutively enrolled subjects across both studies (with a minimum of 50% of subjects enrolled from in the US) will comprise the primary analysis cohort and will be submitted to support a Premarket Notification 510(k) application.

Justification of poolability is based on the following: The Mini S Study and the FORWARD PAD IDE Study protocols share the same eligibility criteria, data collection requirements and IVL treatment algorithm; both studies utilize the same electronic data capture system, are monitored with 100% source document verification, and include an independent angiographic core lab, independent clinical events committee (CEC) for endpoint adjudication of MAE and data safety monitor (DSM); and both studies use the XTR and FLX configurations of the JAVELIN catheter.

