8. ANALYSIS SET

The primary analysis cohort will be the first 90 consecutively enrolled evaluable subjects across both studies (with a minimum of 50% of patients from the US), which will be submitted to support a Premarket Notification 510(k) application.

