9. STATISTICAL METHODS OF ANALYSES

9.1. General Considerations

Descriptive statistics will be provided in this clinical study. Analyses will be reported on at pre-specified time points including 30 days, 6, and 12 months.

Categorical variables will be summarized by the number of non-missing observations, and the frequency and percentage for each category. Unless otherwise noted, missing data will be excluded from the denominator.

Continuous variables will be summarized by the mean, standard deviation, median, IQR, minimum, and maximum.

Statistical analyses will be performed using SAS System® Version 9.4 or higher.

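### SAP Appendix A drops a target lesion with no readable final angiogram from primary Technical Success whatever the reason, so a procedure that fails before the final cine is not counted as a failure

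*SAP*

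**What the plan says.** SAP section 4.2 defines Technical Success by the core lab's reading of the target lesion at the end of the procedure: at most 50% residual stenosis and no dissection of Grade D or worse. Protocol 9.2.2 makes the lesion the unit of analysis.

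SAP Appendix A, part B (Core Lab Endpoints), says how a missing reading is handled. It covers endpoints "such as restenosis measured by duplex ultrasound or residual stenosis by angiography". If the scheduled assessment was not done, or its images could not be read, "it will be treated as missing value and excluded from the analysis".

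The rest of the plan agrees:

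- SAP 9.1: "Unless otherwise noted, missing data will be excluded from the denominator".
- SAP 9.3: "No imputation of or adjustments for missing data will be performed for the primary analyses". Protocol 9.5 says the same.
- SAP 8: "The primary analysis cohort will be the first 90 consecutively enrolled evaluable subjects across both studies". Appendix A part A explains what evaluable means for clinical endpoints, by date of last contact. Nothing explains it for Technical Success.
- SAP 10.2: missing endpoint data are queried until confirmed irretrievable. It does not say how the lesion is then counted.

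Protocol 9.4 names as primary population "the Intent-to-Treat (ITT) cohort which includes all enrolled subjects". The intent-to-treat sentence in the SAP stands in section 6.1, which concerns safety; section 6.2, on effectiveness, has no counterpart.

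**The concern.** A lesion is enrolled once the catheter is in the body (Protocol 7.7.4), so procedures that go badly are in the study. The final cine is taken only after all endovascular work on the lesion is finished (Protocol 7.7.10). If a procedure is stopped, converted to surgery or ends in death before then, the lesion has not reached Technical Success, yet under Appendix A part B it has no final reading and is removed.

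For clinical endpoints the plan guards against this kind of loss: SAP 9.3 and Appendix A keep a subject with an event in the denominator even when follow-up is short. Core lab endpoints have no matching rule. Appendix A part C does settle components before the composite, but only for primary patency.

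Dropping such a lesion can only raise the observed success rate, and this is one of the two tests that decide study success.

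**Working it through.** **Inputs.** SAP 6.2 and 6.3: performance goal 85.0%, expected rate 97.0%, one-sided alpha 0.025, exact binomial test, N = 90, stated power 98.1%. The documents give no rate of missing final cines, so that is an assumption, shown as a range. All figures take 90 independent lesions, one per subject.

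**1. The plan's own figure.** The goal is met with s successes in n lesions if P(X ≥ s | n, 0.85) ≤ 0.025. For n = 90:

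- P(X ≥ 83) = 0.0308, too large.
- P(X ≥ 84) = 0.0131, so the rule is 84/90 or better, that is at most 6 failures.
- Power is P(X ≥ 84 | 90, 0.97) = 0.9812, which reproduces the stated 98.1%.

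This calculation allows for no missing lesions.

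**2. Effect of dropping failures at the boundary.** Successes stay fixed; each dropped failure takes one lesion from n. Lower limits are exact two-sided 95%.

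| True failures in 90 | All counted | Failures dropped | Result after dropping |
|---|---|---|---|
| 7 | 83/90, p = 0.0308, lower limit 84.6%, goal missed | 1 | 83/89, p = 0.0145, lower limit 85.9%, goal met |
| 8 | 82/90, p = 0.0632, goal missed | 2 | 82/88, p = 0.0160, goal met |
| 9 | 81/90, p = 0.1153, goal missed | 3 | 81/87, p = 0.0177, goal met |

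**3. Effect on Type I error.** Let q be the assumed share of failures with no readable final cine, with every success readable. At a true rate of 85%, failures F ~ Bin(90, 0.15) and dropped lesions M given F ~ Bin(F, q). The goal is met if P(X ≥ 90 − F | 90 − M, 0.85) ≤ 0.025. Summing over F and M gives the middle column.

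If evaluable in SAP 8 means that unread cases are replaced until 90 are readable, the apparent success rate becomes 0.85 / (0.85 + 0.15(1 − q)). At q = 10% that is 0.85/0.985 = 0.8629, and P(X ≥ 84 | 90, 0.8629) = 0.0288.

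| q (assumed) | 90 enrolled, unread dropped | Replaced to 90 readable |
|---|---|---|
| 0 | 0.0131 | 0.0131 |
| 5% | 0.0209 | 0.0195 |
| 10% | 0.0325 | 0.0288 |
| 20% | 0.0730 | 0.0609 |
| 30% | 0.1444 | 0.1223 |

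The nominal 0.025 is still respected at 5% and exceeded at 10%, in both versions.

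**4. Effect of counting them.** If lesions without a final cine because of procedural failure stay in as failures, the rule remains 84/90, attained alpha 0.0131 and power 98.1%.

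Scoring every unread lesion as a failure is harsher. If a share u of final cines is missing for unrelated reasons, the expected rate becomes 0.97(1 − u). Power is then 93.3% at u = 1%, 84.3% at 2% and 71.8% at 3%. The blanket rule therefore belongs in a sensitivity analysis.

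**The case against.** The best answer is that this will hardly ever happen. Protocol 7.7.1 requires a final cine for each target lesion. After an IVL Device Failure, treatment continues (Protocol 7.7.5 and 7.7.6), so device failure alone does not remove the image. Acute closure is itself defined by angiography (Protocol 15.1). Missing endpoint data are queried. Protocol 3.1.3 reports a final residual stenosis for all of the first 11 Mini S subjects. All of this stands as a reason to expect few cases. It does not say how a case is counted.

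Bad outcomes are also visible elsewhere. Perforation, distal embolization, closure and Grade D or worse dissection form a secondary endpoint, and dissections of Grades D to F must be recorded as SAEs. That limits the problem to the primary effectiveness denominator, which is where it matters for study success.

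The reversal in step 2 needs results near the boundary. At the planned 97%, expected failures are 90 × 0.03 = 2.7 and 6 are allowed. The chance of 7 or more is 1 − 0.9812 = 1.9%, and with q = 10% the chance of meeting the goal rises only from 98.1% to 98.9%. The cutoff also moves with the number of lesions: with 93 to 100 lesions, 7 failures pass, and up to two lesions per subject are allowed. These are fair limits. The bias matters when the true rate is well below 97%, which is the case that a test against 85% is meant to catch.

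A reader might also infer a flat contradiction with the intent-to-treat population of Protocol 9.4. The documents do not support that. Protocol 9.5 already pairs this population with no imputation, and SAP section 2 says that it may supersede the protocol's statistical plan. There is a tension over who counts, no more. Nor is a lesion with a readable post-dilatation cine but an unreadable final one lost altogether: it still counts in the secondary endpoint IVL Technical Success (post-dil).

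**Conclusion.** The point holds. Appendix A part B is a stated rule, it names angiographic residual stenosis, and it has no exception by reason. A lesion whose procedure failed before the final cine would be removed from the primary effectiveness test, and the error favours meeting the goal.

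The size depends on an unknown. One dropped failure changes the verdict at 7 failures in 90, which is a boundary illustration and not a forecast. Type I error passes 0.025 somewhere between q = 5% and q = 10%, assuming that only failures go unread and that the 90 lesions are independent.

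A reader might go further and infer that missing final cines will mostly be failures, or that the effectiveness result will be wrong. The documents do not support that: stopped, converted or fatal procedures are inferred from a rule without exceptions, and no frequency is given. The stated power of 98.1% is correct; the fault lies in the handling rule and not in the sample size.

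**What to change.** Before database lock, revise the SAP as follows.

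1. In Appendix A part B, state that for Technical Success a target lesion in an enrolled subject with no evaluable final cine because the procedure was stopped, converted to surgery or ended in death is a failure and stays in the denominator.
2. In section 8, make clear that the word evaluable does not remove such subjects from the primary analysis cohort.
3. Add a sensitivity analysis of Technical Success that scores every target lesion without a final reading as a failure, whatever the reason, and report the number of such lesions with reasons.

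Carrying the post-dilatation cine forward into the primary endpoint would not be a good substitute. It replaces the final result with the state before any destination therapy. A lesion later treated successfully could be scored a failure, and one dissected during later treatment could be scored a success.

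The cost is a few sentences of SAP text, one extra table and a possibly slightly lower success rate. No new data are needed. With item 1 alone the decision rule stays at 84/90, and power stays at 98.1% if only true failures are affected.
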